## **16.6 Results Reporting on ClinicalTrials.gov**

At study activation, this study will have been registered within the “ClinicalTrials.gov” website. The Primary and Secondary Endpoints along with other required information for this study will be reported on [www.ClinicalTrials.gov](http://www.ClinicalTrials.gov). For purposes of timing of the Results Reporting, the initial estimated completion date for the Primary Endpoint of this

study is 4 years after the study opens to accrual. The definition of “Primary Endpoint Completion Date” (PECD) for this study is at the time all patients registered have completed 24 cycles of treatment or have discontinued treatment before the completion of 24 cycles.

### 16.7 Subset Analyses for Minorities

#### 16.71 Study availability

This study will be available to all eligible patients, regardless of gender, race or ethnic origin.

#### 16.72 Statistical analysis by subset

There is no information currently available regarding differential effects of this regimen in subsets defined by race, gender, or ethnicity, and there is no reason to expect such differences to exist. Therefore, although the planned analysis will, as always, look for differences in treatment effect based on racial and gender groupings, the sample size is not increased in order to provide additional power for subset analyses.

#### 16.73 Regional population

The geographical region served by MCCC has a population which includes approximately 3% minorities. Based on prior MCCC studies involving similar disease sites, we expect about 3-5% of patients will be classified as minorities by race and about 20% of patients will be women.

### Accrual Estimates by Gender/Ethnicity/Race

Ethnic Category	Sex/Gender			
	Females	Males	Unknown	Total
Hispanic or Latino	0	1	0	1
Not Hispanic or Latino	9	37	0	46
Ethnic Category: Total of all patients*	9	38	0	47
Racial Category				
American Indian or Alaskan Native	0	0	0	0
Asian	0	0	0	0
Black or African American	0	1	0	1
Native Hawaiian or other Pacific Islander	0	0	0	0
White	9	37	0	46
Racial Category: Total of all patients*	9	38	0	47

**Ethnic Categories:** **Hispanic or Latino** – a person of Cuban, Mexican, Puerto Rican, South or Central American, or other Spanish culture or origin, regardless of race. The term “Spanish origin” can also be used in addition to “Hispanic or Latino.”  
**Not Hispanic or Latino**

**Racial Categories:**

**American Indian or Alaskan Native** – a person having origins in any of the original peoples of North, Central, or South America, and who maintains tribal affiliations or community attachment.

**Asian** – a person having origins in any of the original peoples of the Far East, Southeast Asia, or the Indian subcontinent including, for example, Cambodia, China, India, Japan, Korea, Malaysia, Pakistan, the Philippine Islands, Thailand, and Vietnam. (Note: Individuals from the Philippine Islands have been recorded as Pacific Islanders in previous data collection strategies.)

**Black or African American** – a person having origins in any of the black racial groups of Africa. Terms such as “Haitian” or “Negro” can be used in addition to “Black or African American.”

**Native Hawaiian or other Pacific Islander** – a person having origins in any of the original peoples of Hawaii, Guam, Samoa, or other Pacific Islands.

**White** – a person having origins in any of the original peoples of Europe, the Middle East, or North Africa.

**17.0 Pathology Considerations/Tissue Biospecimens**

**17.1** None.

**18.0 Records and Data Collection Procedures****18.1** Submission Timetable

Data submission instructions for this study can be found in the Data Submission Schedule.

**18.2** Survival Follow-up

See [Section 4.2](#)

**18.3** CRF completion

This study will use Medidata Rave for remote data capture (rdc) of all study data. Data collection for this study will be done exclusively through the Medidata Rave clinical data management system. Access to the trial in Rave is granted through the iMedidata application to all persons with the appropriate roles assigned in Regulatory Support System (RSS). To access Rave via iMedidata, the site user must have an active account and the appropriate Rave role (Rave CRA, Read-Only, Site Investigator) on either the organization roster at the enrolling site.

**18.4** Site responsibilities

Each site will be responsible for insuring that all materials contain the patient's initials, MCCC registration number, and MCCC protocol number. Patient's name must be removed.

**18.5** Supporting documentation

This study requires supporting documentation for diagnosis, response to previous treatment with ibrutinib, and last date of ibrutinib treatment prior to study entry as well as for evidence of response to study therapy and progression after study therapy. Supporting documentation for diagnosis will include a pathology report and a laboratory report demonstrating Waldenström macroglobulinemia (including serum quantitative immunoglobulins, SPEP, UPEP, FLC, Serum and Urine Immunofixation, Bone Marrow Biopsy and Aspirate, CT/PET scan,). These reports should be uploaded into the Supporting Documentation: Baseline form within 14 days of registration.

For response to treatment, supporting documentation may include serum quantitative immunoglobulins, SPEP, UPEP, FLC, Serum and Urine Immunofixation, Bone Marrow Biopsy and aspirate, and PET scan. These documents should be uploaded into the Supporting Documentation form.

For patients who progress after study therapy supporting documentation may include any of the following: serum quantitative immunoglobulins, SPEP, UPEP, FLC, serum and urine immunofixation, bone marrow biopsy and aspirate, and PET/CT scan. These documents should be uploaded into the Supporting Documentation form

**18.6** Labeling of materials

Each site will be responsible for insuring that all materials contain the patient's initials, MCCC registration number, and MCCC protocol number. Patient's name must be removed.

**18.7** Overdue lists

A list of overdue forms and outstanding queries will be available in Rave through the Rave Task Summary. In addition to this, the Overdue Materials report is available on the Cancer Center Systems homepage.

## **19.0    Budget**

- 19.1**    Costs charged to patient: routine clinical care, ibrutinib
- 19.2**    Tests to be research funded: ixazomib is provided by Takeda (Millennium) Pharmaceuticals, Inc, Bone Marrow Biopsy aspirate at Cycle 2 Day 1, personnel effort, statistics, and research correlatives.

**Appendix I ECOG Performance Status****ECOG PERFORMANCE STATUS\***

Grade	ECOG
0	Fully active, able to carry on all pre-disease performance without restriction
1	Restricted in physically strenuous activity but ambulatory and able to carry out work of a light or sedentary nature, e.g., light house work, office work
2	Ambulatory and capable of all selfcare but unable to carry out any work activities. Up and about more than 50% of waking hours
3	Capable of only limited selfcare, confined to bed or chair more than 50% of waking hours.
4	Completely disabled. Cannot carry on any selfcare. Totally confined to bed or chair.
5	Dead

\*As published in Am. J. Clin. Oncol.:

The ECOG Performance Status is in the public domain therefore available for public use. To duplicate the scale, please cite the reference above and credit the Eastern Cooperative Oncology Group, Robert Comis M.D., Group Chair.

From [http://www.ecog.org/general/perf\\_stat.html](http://www.ecog.org/general/perf_stat.html)

## Appendix II Patient Medication Diary

Name \_\_\_\_\_ Study ID Number \_\_\_\_\_

Please complete this diary on a daily basis. Please bring your dosing diary to your next scheduled appointment. Write in the amount of the dose of ixazomib and ibrutinib that you took in the appropriate “Day” box. On the days that you do not take any study drug, please write in “0”. If you forget to take your daily dose, please write in “0” and do not make up this missed dose. Remember to take your prescribed dose at the next regularly scheduled time.

Please store the ixazomib as indicated on the bottle. Ixazomib should be taken on an empty stomach (either 1 hour before or 2 hours after meals) with 8 oz. of water. Swallow the capsules whole; do not open, break, or chew the capsules. If you experience a vomiting episode in the same day after taking ixazomib, do not make up this dose. Please indicate the time you took the drug and the time you vomited.

Ibrutinib should be taken with water at approximately the same time each day and can be taken with or without food. Swallow the capsules whole; do not open, break, or chew the capsules. Please avoid grapefruit and Seville oranges during your ibrutinib treatment. Supplements such as fish oil and vitamin E preparations should also be avoided.

If you experience any health/medical complaints or take any medication other than ixazomib and ibrutinib please record this information.

Study Drug(s)	Dose	Study Coordinator only: Write in the dose assigned by the study doctor in this column if different than the dose listed in the previous column
Ibrutinib	420 mg	
Ixazomib	4mg	

Week of:

Study Drug	Day 1	Day 2	Day 3	Day 4	Day 5	Day 6	Day 7
Date							
Ixazomib							
Ibrutinib							

Week of:

Study Drug	Day 8	Day 9	Day 10	Day 11	Day 12	Day 13	Day 14
Ixazomib							
Ibrutinib							

Week of:

Study Drug	Day 15	Day 16	Day 17	Day 18	Day 19	Day 20	Day 21
Ixazomib							
Ibrutinib							

Week of:

Study Drug	Day 22	Day 23	Day 24	Day 25	Day 26	Day 27	Day 28
-------------------	---------------	---------------	---------------	---------------	---------------	---------------	---------------

Ixazomib							
Ibrutinib							

Patient signature: \_\_\_\_\_

**Health or medical complaints during this time:**

**Other medications or supplements taken during this time:**

Name of medication or supplement	How much did you take? (example: Two 500mg pills)	When did you take it (examples: Every day Or Day 19 and Day 20)

Use a separate sheet of paper if more space is needed.

**My next scheduled visit is:** \_\_\_\_\_

If you have any questions, please call: \_\_\_\_\_

**Study Coordinator Use Only**

Number of pills returned \_\_\_\_\_  
Discrepancy Yes \_\_\_\_\_ / No \_\_\_\_\_

Number of vials returned: \_\_\_\_\_  
Verified by \_\_\_\_\_ Date \_\_\_\_\_

### Appendix III Response Assessment Criteria

Response	Criteria
Complete response	
 
• Absence of serum monoclonal IgM protein by immunofixation
 
• Normal serum IgM level
 
• Complete resolution of extramedullary disease, i.e., lymphadenopathy (resolution to <math>\leq 1.5</math> cm in longest diameter of all nodes) and splenomegaly/hepatomegaly if present at baseline
 
• Morphologically normal bone marrow aspirate and trephine biopsy
 
• No signs or symptoms attributable to WM
 
 
Confirmation of the complete response status is required on two consecutive evaluations with a second immunofixation before reporting an objective status of CR

Very good partial response	
 
• Monoclonal IgM protein is detectable
 
• <math>\geq 90\%</math> reduction in serum IgM level from baseline
 
• Complete resolution of extramedullary disease, i.e., lymphadenopathy (resolution to <math>\leq 1.5</math> cm in longest diameter of all nodes) and splenomegaly/hepatomegaly if present at baseline
 
• No new signs or symptoms of active disease
 

Partial response	
 
• Monoclonal IgM protein is detectable
 
• <math>\geq 50\%</math> but <math>< 90\%</math> reduction in serum IgM level from baseline
 
• <math>\geq 50\%</math> reduction in extramedullary disease, i.e., <math>\geq 50\%</math> reduction in SPD from baseline for lymphadenopathy and <math>\geq 50\%</math> reduction from baseline in splenomegaly/hepatomegaly if present at baseline
 
• No new signs or symptoms of active disease
 

Minor response	
 
• Monoclonal IgM protein is detectable
 
• <math>\geq 25\%</math> but <math>< 50\%</math> reduction in serum IgM level from baseline
 
• No new signs or symptoms of active disease
 

Stable disease	
 
• Monoclonal IgM protein is detectable
 
• <math>< 25\%</math> reduction and <math>< 25\%</math> increase in serum IgM level from baseline
 
• No progression in extramedullary disease, i.e., lymphadenopathy/splenomegaly/hepatomegaly
 
• No new signs or symptoms of active disease
 

Progressive disease 	
 
• <math>\geq 25\%</math> increase in serum IgM level from lowest nadir confirmed by a second measurement 4 weeks apart and/or progression in clinical features attributable the disease (i.e., anemia, thrombocytopenia, leukopenia, bulky adenopathy/ organomegaly)
 
or
 
• symptoms attributable to WM (unexplained recurrent fever <math>\geq 38.4^{\circ}\text{C}</math>, drenching night sweats, <math>\geq 10\%</math> body weight loss, hyperviscosity, neuropathy, symptomatic cryoglobulinemia, or amyloidosis)
 
or
 
• Transformation to a more aggressive histology
 
or
 
• Progression criteria for lymphadenopathy: In patients who achieved PR, MR, or SD an increase of <math>\geq 25\%</math> from the nadir in the SPD of any previous lymph nodes or appearance of a new lymph node (that must be <math>></math>
 

2 cm). For patients who have **achieved a VGPR or CR**, progression will be defined as appearance of a new lymph node (that must be  $\geq 2$  cm).

- Progression criteria based upon splenic or hepatic enlargement: In patients who **achieved PR, MR, or SD** an increase in the size of the spleen and / or liver of  $\geq 25\%$  from the nadir. For patients who have **achieved a VGPR or CR**, progression will be defined if there is increase in the size of spleen and / or liver that is  $\geq 25\%$  the upper limit of normal measured in the longitudinal axis.

 In the case where progression is first observed, the objective status will be entered as unconfirmed progression (uPD) on the measurement form. Once this criterion is confirmed at least 4 weeks later, the objective status will be entered as PD. If confirmed, the date of first evidence of progression (date of first uPD) will be considered the progression date (and should be entered on the event monitoring form).

 If IgM alone is used to determine progression, there must be  $\geq 500$  mg/dL increase in IgM from the nadir. (Owen, 2013)

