## 1.0 Background

### 1.1 Waldenström macroglobulinemia

Waldenström macroglobulinemia (WM) is an incurable indolent B-cell neoplasm manifested by the accumulation of clonal immunoglobulin (Ig)M-secreting lymphoplasmacytic cells (Treon, Xu et al. 2015). WM is a rare disorder, with an incidence rate of about 3 cases per million people per year in the United States (ACS website).

**Clinical Presentation:** patients may have variable clinical presentation and the symptoms can be divided into three major clinical groups: (a) symptoms related to the underlying lymphoproliferative process (e.g., constitutional symptoms, cytopenias, or tissue infiltration), (b) hyperviscosity related to the overproduction of IgM, and (c) paraneoplastic neuropathy.

Patients with disease-related hemoglobin <10 g/L, platelets <100 × 10^9/L, bulky adenopathy and/or organomegaly, symptomatic hyperviscosity, peripheral neuropathy, amyloidosis, cryoglobulinemia, cold-agglutinin disease, or transformed disease are often considered for therapy while asymptomatic patients can be monitored.

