## 9.0 Ancillary Treatment/Supportive Care

### 9.1 Full supportive care

Patients should receive full supportive care while on this study. This includes blood product support, antibiotic treatment, and treatment of other newly diagnosed or concurrent medical conditions. All blood products and concomitant medications such as antidiarrheals, analgesics, and/or antiemetics received from the first day of study treatment administration until 30 days after the final dose will be recorded in the medical records.

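### Appendix III does not exclude IgM values lowered by plasma exchange, so an exchange can be scored as PR or can set an artificial nadir that later yields a false PD

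*Combined protocol and SAP*

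**What the plan says.** **Response.** Appendix III requires for PR a 50% to under 90% "reduction in serum IgM level from baseline". VGPR needs at least 90%, and MR 25% to under 50%. PR also needs any baseline extramedullary disease to have halved, and "No new signs or symptoms of active disease". Confirmation is required for CR only: "Confirmation of the complete response status is required on two consecutive evaluations with a second immunofixation before reporting an objective status of CR". Section 16.321 counts CR, VGPR and PR towards ORR.

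**Progression.** The biochemical criterion is a 25% or greater "increase in serum IgM level from lowest nadir confirmed by a second measurement 4 weeks apart". Footnote 2 adds a floor: "If IgM alone is used to determine progression, there must be" a rise of at least 500 mg/dL from the nadir. Under footnote 1, once PD is confirmed, "the date of first evidence of progression (date of first uPD) will be considered the progression date". Section 13.2 then moves the patient to survival follow-up, and Section 16.322 counts a TTP event.

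**Hyperviscosity and supportive care.** Section 1.1 lists "hyperviscosity related to the overproduction of IgM" among three symptom groups and names symptomatic hyperviscosity as a reason to consider therapy. Section 3 does not exclude it, and Section 4.1 schedules serum viscosity. Section 9.1 states: "Patients should receive full supportive care while on this study". Section 9.5 allows ancillary treatment on medical need and asks for it to be recorded in the chart and on the CRF. The supplied text mentions plasma exchange nowhere, either to permit it, to forbid it, or to say how IgM is handled afterwards.

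**The concern.** The premise, which the documents do not state, is that plasma exchange removes IgM from the blood without acting on the disease. An IgM value taken soon afterwards then reflects the procedure, and Appendix III gives no ground for setting it aside.

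Two errors can follow. If the value is at least 50% below baseline, the patient can be scored PR on one assessment. At any depth, the value can become the nadir. When IgM climbs back towards the level that the drugs alone would give, the climb can meet the progression criterion. The patient then has a TTP event and leaves protocol treatment although the disease has not progressed.

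**Working it through.** **1. The plan's own figures.** With p the true CR rate, P(promising) = Σ over x = 1 to 12 of Bin(x; 12, p) × P(Bin(25, p) ≥ 4 − x). This gives 0.0935 at p = 0.05 and 0.902 at p = 0.20, matching the stated 0.09 and 0.90 in Section 16.24. The design table is sound; the issue is how patients are classified.

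**2. Inputs.** The 50%, 25% and 500 mg/dL limits come from Appendix III, and 37 evaluable patients from Section 16.21. The fractional IgM fall d due to exchange is not in the documents; I assume 20% to 70%.

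**3. Exchange alone, then full return to baseline B.** The nadir is (1 − d)B. The rise from nadir is d/(1 − d). The absolute rise is dB, so the floor is met when B ≥ 500/d. The 25% limit is reached at 1.25(1 − d)B.

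| Fall d | IgM category at nadir | Rise at full return | B needed for the 500 mg/dL floor at full return | +25% reached at (% of B) |
|---|---|---|---|---|
| 20% | SD | 25% | 2,500 | 100% |
| 30% | MR | 42.9% | 1,667 | 87.5% |
| 40% | MR | 66.7% | 1,250 | 75% |
| 50% | PR | 100% | 1,000 | 62.5% |
| 60% | PR | 150% | 833 | 50% |
| 70% | PR | 233% | 714 | 37.5% |

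A false PR from exchange alone therefore needs d ≥ 50%. A false PD can arise at smaller falls, and above 20% the 25% limit is met before IgM is back at baseline.

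**4. Worked cases, B = 5,000 mg/dL.**
- Fall of 50% to 2,500: meets the PR limit. Return to 3,500: 3,500/2,500 = +40%, and +1,000 mg/dL, so PD. Yet 3,500/5,000 is a 30% fall from baseline, in the MR range.
- Fall of 30% to 3,500: MR only, so ORR is unchanged. Return to 4,500: 4,500/3,500 = +28.6%, and +1,000 mg/dL, so PD, still 10% below baseline.

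**5. Exchange on top of a drug effect.** Let the drugs alone hold IgM at gB. The exchange fall needed to reach the PR limit is 1 − 0.5/g, and the rise on return to gB is g/0.5 − 1. At g = 0.8 these are 37.5% and 60%. At g = 0.6 they are 16.7% and 20%, so a false PR can still occur but the return does not reach 25%.

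**6. Confirmation.** Once IgM has returned, a second value 4 weeks later is still above the lowered nadir. Confirmation guards against measurement noise, not against a wrong reference value, and the date goes back to the first rise.

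**7. Baseline.** IgM is drawn up to 14 days before registration, none is scheduled on Cycle 1 Day 1 (Section 4.1), and treatment may start up to 28 days after registration (Section 6.6). The gap can be 14 + 28 = 42 days, and an exchange within it would be credited to the drugs.

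**8. Size.** One false PR moves ORR by 1/37 = 2.7 points.

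**The case against.** The case against has several parts, and much of it stands as a limit on scope.

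- **The criteria have thresholds.** A reader might infer that any fall after exchange counts as response and any rise as progression. They do not: PR needs 50% plus the extramedullary and symptom conditions, and IgM-only PD needs 25%, 500 mg/dL and confirmation. Nor can exchange alone give VGPR within the assumed range, since that needs 90%.
- **Hyperviscosity is itself listed under PD.** New hyperviscosity attributable to WM can count as progression in its own right, and new symptoms bar PR. Exchange for hyperviscosity that first appears on study may therefore be scored PD correctly.
- **Events must coincide.** The lowered value must fall on an assessment, and IgM must then stay above the limits while the patient takes both drugs. Section 1.2 reports 61.9% response and a median of 1.2 months to response for ibrutinib alone. With a nadir of 2,500 from 5,000, a patient whose drug-controlled IgM is at or below 2,500 never reaches the PD level of 3,125. False PD mainly concerns slower or lesser responders.
- **Recording is partly in place.** Section 9.5 already sends ancillary treatments to the CRF.
- **Exchange might be thought barred.** Section 9.5 prohibits other anticancer treatments, but the plan does not say that this covers exchange.

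None of this supplies a rule for the value itself. A patient with hyperviscosity at entry who is exchanged before or early in treatment can be misclassified by following Appendix III exactly.

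**Conclusion.** The gap is real and limited in reach. It bears mainly on two secondary endpoints: ORR, by 2.7 points per false PR, and TTP, by one false event per false PD.

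A reader might infer that the primary decision, at 4 of 37, is directly exposed. The documents do not support that. CR needs negative immunofixation, normal IgM, a normal marrow and confirmation on two consecutive evaluations, so a false CR is implausible. The remaining route is a patient removed for false PD who would later have reached CR. At the 20% target rate that is about 0.2 expected successes per such patient, and probably fewer, because those at risk are the lesser responders.

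The conclusion rests on two assumptions: that exchange lowers IgM appreciably (20% to 70% was examined) and that some patients are exchanged. The documents give neither the size of the fall nor the number of patients, so no total effect on ORR or TTP can be stated.

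**What to change.** Make this an analysis rule only; it need not affect whether or when exchange is given.

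1. Add a footnote to Appendix III: IgM values within a pre-stated window after plasma exchange are not used for response, nadir or IgM-based progression. The study team sets the window; the documents offer no basis for a particular length. The other progression criteria continue to apply.
2. If an exchange falls between the baseline IgM and the first dose, use a pre-dose IgM taken after the exchange as baseline. That value may itself be lowered, which understates later falls. While it lies inside the window it should not serve as the nadir.
3. Capture exchange dates as an explicit item on the ancillary-treatment CRF that Section 9.5 already calls for.

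The cost is one footnote, one CRF item and, for affected patients, one extra pre-dose IgM. Some response or progression calls will come a cycle later, or later still with repeated exchanges, which could leave several consecutive IgM assessments unusable.

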#### 4.2 Survival Follow-up

Survival Follow-up 				
	Every 3 months until disease progression or subsequent treatment	At disease progression or initiation of subsequent therapy	Every 6 months after disease progression or initiation of subsequent therapy	At death
Event Monitoring	X	X	X	X

1. If a patient is still alive 5 years after registration, no further follow-up is required.

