**16.32 Secondary Outcome Analysis**

16.321 The overall response rate will be estimated by the total number of patients who achieve a CR VGPR, or PR divided by the total number of evaluable patients. All evaluable patients will be used for this analysis. Exact binomial 95% confidence intervals for the true overall response rate will be calculated.

16.322 Time to progression is defined as the time from registration to the earliest date of documentation of disease progression. The distribution of time to progression will be estimated using the method of Kaplan-Meier.

16.323 Overall survival is defined as the time from registration to death due to any cause. The distribution of overall survival will be estimated using the method of Kaplan-Meier.

16.324 AEs: All eligible patients that have initiated treatment will be considered evaluable for assessing AE rate(s). The maximum grade for each type of AE will be recorded for each patient, and frequency tables will be reviewed to determine patterns. Additionally, the relationship of the AE(s) to the study treatment will be taken into consideration.

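### Appendix III footnote 1 requires 4-week confirmation of every type of progression, and Section 16.322 does not say how a progression that can never be confirmed enters TTP, so TTP could be overstated

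*Combined protocol and SAP*

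**What the plan says.** Appendix III lists several routes to PD. The IgM route carries its own repeat: an "increase in serum IgM level from lowest nadir confirmed by a second measurement 4 weeks apart". The other routes carry no confirmation wording in the row: "Transformation to a more aggressive histology", symptoms due to Waldenström macroglobulinemia (WM), nodal growth, and enlargement of the spleen or liver.

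Footnote 1 is marked on the PD heading, so on a plain reading it governs the whole row. It says "In the case where progression is first observed, the objective status will be entered as unconfirmed progression (uPD) on the measurement form", then "Once this criterion is confirmed at least 4 weeks later, the objective status will be entered as PD". On dating it says "If confirmed, the date of first evidence of progression (date of first uPD) will be considered the progression date", and that date is the one to be entered on the event monitoring form. It makes no exception for transformation, new therapy or death.

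Section 16.322 states: "Time to progression is defined as the time from registration to the earliest date of documentation of disease progression". The curve is estimated by Kaplan-Meier. The section does not say whether uPD is documentation of progression. It gives no censoring rule for new therapy, death or loss, and death is not a TTP event.

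Patients who progress go to survival follow-up (Sections 13.2 and 13.3). The only item scheduled there is event monitoring, first "Every 3 months until disease progression or subsequent treatment", then at either of those events, then every 6 months (Section 4.2).

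**The concern.** The row and the footnote give different rules for the non-IgM criteria. If the footnote is followed literally, a patient who starts new WM therapy, dies or is lost before a repeat assessment has no route from uPD to PD and no assigned progression date. New therapy may reverse IgM or nodal findings before anyone can confirm them, and a tissue diagnosis of transformation may not be repeated.

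The progressions most exposed are those that prompt the fastest switch of therapy or lead to early death. If they drop out of the event count, the censoring is related to outcome and the Kaplan-Meier TTP curve is pushed upward. TTP is a stated secondary goal (Section 2.2), and a single-arm trial has no comparator in which the same bias would occur.

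**Working it through.** **Step 1: follow a first progression through the rules.**

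| After the first uPD | Status (footnote 1) | Date assigned (footnote 1) | TTP (Section 16.322) |
|---|---|---|---|
| Confirmed at least 4 weeks later | PD | First uPD | Event on the uPD date |
| New therapy, death or loss before reassessment | Stays uPD | None, since the date depends on confirmation | Not stated |

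The first line shows that the wait alone adds no time to TTP. The problem is confined to the second line.

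**Step 2: inputs.** The plan gives no TTP median, target or test, so there is no TTP figure to reproduce. Let f be the fraction of true progressions never confirmed. It is not in the documents; 10% to 30% is assumed here. Exponential TTP with hazard λ is also assumed, as are true 24-month progression-free proportions S of 60%, 75% and 90%. The number of evaluable patients, 37, is from Section 16.21.

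**Step 3: three ways the analyst could treat these patients.**

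- *A. Censored at uPD.* The estimated hazard is (1−f)λ, so the median is multiplied by 1/(1−f) and the 24-month estimate becomes S^(1−f).
- *B. Left in the risk set without an event.* The estimated curve is 1−(1−f)(1−S(t)). The median is multiplied by −ln(1−0.5/(1−f))/ln 2.
- *C. uPD counted as an event on its own date.* Nothing changes; the multiplier is 1.

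| f | Median, A | Median, B | 24-month, true 60% (A / B) | 24-month, true 75% (A / B) | 24-month, true 90% (A / B) |
|---|---|---|---|---|---|
| 10% | 1/0.9 = 1.11 | 1.17 | 63.1% / 64.0% | 77.2% / 77.5% | 91.0% / 91.0% |
| 20% | 1/0.8 = 1.25 | 1.42 | 66.5% / 68.0% | 79.4% / 80.0% | 91.9% / 92.0% |
| 30% | 1/0.7 = 1.43 | 1.81 | 69.9% / 72.0% | 81.8% / 82.5% | 92.9% / 93.0% |

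A Kaplan-Meier simulation (37 patients, 2,000 runs, follow-up cut at 60 months) agrees. At f = 20% and a true 60% it gives 66.5% (A) and 68.0% (B); at a true 75% it gives 79.5% and 80.1%.

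**Step 4: what f means in patients.** If 25% of 37 patients progress by 24 months, that is 0.25 × 37 = 9.25, about 9 events. One progression left unconfirmed is then 1/9, or about 11%.

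**The case against.** A reader might infer that TTP is overstated as a matter of fact, or that the 4-week wait lengthens it. The documents do not support either reading.

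- **Backdating.** Confirmed PD takes the date of the first uPD, so the wait is harmless when confirmation happens. This stands.
- **Section 16.322 does not exclude uPD.** TTP runs to documented progression, not to a status code on the measurement form, and footnote 1 itself treats the first uPD as the first evidence of progression. A biopsy-proven transformation could reasonably be counted. This stands as a possible reading, but the plan does not adopt it.
- **Other records may capture the event.** Reason 4 on the Off Treatment Form (Section 13.0) is disease progression. Section 18.5 accepts a marrow report or PET/CT as support for progression and asks for no repeat. Event monitoring is triggered by new therapy as well as by progression. This stands in part: no section says which record governs TTP, and footnote 1 ties the event-monitoring date to confirmation. One patient could be uPD on one form and progressed on another.
- **Reassessment often remains possible.** A uPD that is not yet PD does not by itself end protocol treatment under Section 13.2, so scheduled tests continue. Section 13.3 asks for end-of-treatment procedures after an early stop, and that visit includes immunoglobulins, electrophoresis and tumor measurement. Only patients who switch, die or are lost before reassessment are affected, and their number is unknown.
- **Changing the PD criteria themselves.** PD also ends protocol treatment (Sections 13.2 and 13.3). Declaring the non-IgM criteria immediate PD would therefore reach beyond the analysis. This stands, and it limits the remedy to the TTP event definition.

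**Conclusion.** The point holds as an unresolved rule with a possible upward bias. The PD row and footnote 1 conflict on which criteria need confirmation, and the plan does not say whether an unconfirmable uPD is a TTP event. If such patients are censored or left event-free, TTP could be overstated. The direction is clear, but the size cannot be determined from the documents.

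Under the exponential assumption with censoring at uPD, the median is inflated by 11% to 43% for f between 10% and 30%. It is inflated more if these patients stay at risk, and not at all if uPDs are counted. If few patients progress, the effect on the 24-month estimate is small: at most 3 percentage points for a true value of 90% at these values of f. TTP is a descriptive secondary endpoint. The complete response decision rule, the sample size of 37 and the significance level are untouched.

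**What to change.** 1. Reconcile the PD row with footnote 1 by stating which criteria need confirmation. This review does not propose when treatment should stop; any effect on Sections 13.2 and 13.3 is for the sponsor to reconcile.
2. For the TTP analysis only, state in Section 16.322 and footnote 1 that a uPD followed by subsequent WM therapy or death before a confirmatory assessment is a TTP event dated at the first uPD.
3. State that in those cases the uPD date is entered on the event monitoring form.

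Two related choices are for the sponsor to state and are not part of the required change: how to treat loss to follow-up after a uPD, and whether to censor at new therapy when there was no uPD. The second can itself be informative.

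The cost is wording and a form instruction, with no new visits and no change to sample size. The downside is that some uPDs that would not have been confirmed will count as events, so TTP may look slightly shorter. The documents give no rate for this. The wording should be settled before TTP is analysed.
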